10. STATISTICAL CONSIDERATIONS

Since this is a proof of concept feasibility study, no power calculation is needed. Based on Dalton, 2011, 10-20% of patients may withdraw from the study before completing treatment. Therefore, we will recruit up to 35 patients meeting inclusion/exclusion criteria until 30 subjects have completed treatment. Descriptive statistics will be used to explore changes in primary and secondary outcomes measures between baseline and end of treatment. Although the primary efficacy measure will be a change in frequency of daily stress leaks between Baseline and Week 14 weeks, response to treatment will also consider secondary efficacy measures (change in frequency of voids per day, urine volume per void, change in 24 hour pad weight, responses to validated questionnaires, changes in UPP measures, changes in sexual function), and change in pelvic floor muscles as measured by MRI. Safety will be reported by the number and type of adverse events reported during treatment. No imputations for missing data will be conducted. There will be no adjustment for multiple testing.

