Statistical Considerations:	
This is a proof of concept feasibility study, so no power calculation is needed. Therefore, up to 35 subjects meeting inclusion/exclusion criteria will be recruited until 30 subjects have completed treatment. Descriptive statistics will be performed to explore changes in primary and secondary outcomes measures between baseline and end of treatment. The primary efficacy measure will be a reduction in the number of stress incontinence episodes/day. Secondary efficacy measures will include reduction in number of voids per day, volume of voids, 24 hour pad weight, responses to validated questionnaires, changes in UPP measures, changes in sexual function, and changes in pelvic floor muscles as measured by MRI.
 
Safety will be determined by the number and type of adverse events reported during treatment. Various imputation methods may be explored.

Study Intervention/Treatment:	
Participation in this study includes 5 in person study visits and two telephone and/or mailed questionnaire visits. Additional in person and/or telephone visits may be added as needed.
 
Study subjects will receive 3 mg of GTx-024 orally daily.

Table 1. Schedule of Measures.

	Screening Visit Days -21-0	Additional Screening Days -21-0	Visit 1. Baseline³ Week 0	Visit 2. Week 1 ± 3 days	Visit 3. Week 4 ± 3 days	Visit 4. Week 8 ± 3 days	Visit 5. Week 12 ± 3 days	Visit 6. Week 16 ± 7 days
	Clinic Visit	Clinic Visit	Clinic Visit	Phone Call	Clinic Visit	Clinic Visit	Clinic Visit	Phone Call and Mail
Consent	x							
Inclusion/Exclusion	x		x					
History			x					
Interview/Vital Signs	x		x		x	x	x	
Height/Weight	x				x	x	x	
24 hour Pad Weight	Instruct		x		x	x	x	
3 day Voiding Diary	Instruct		x		x	x	x	
Serum AST, ALT, Total Bilirubin	x				x	x	x	
Serum FSH ¹ ,	x							
CBC			x				x	
UA Dipstick (with culture as needed)	x		x				x	
Lipid Panel			x				x	
Testosterone Levels			x				x	
SHBG			x				x	
UPP			x				x	
Pelvic MRI		x					x	
Bladder Stress Test	x						x	
Mammogram ²		x						
Begin Daily ⁴ Treatment			x					
End Treatment							x	
Concomitant Meds	x		x	x	x	x	x	x
Adverse Events			x	x	x	x	x	x
HIV, Hep A, B, C Testing	x							
UDI-6; IIQ			x		x	x	x	x
PGI-S			x		x	x	x	x
MESA Questionnaire	x				x	x	x	x
PGI-I					x	x	x	x
FSFI Questionnaire			x		x	x	x	x
Bladder Scan PVR			x		x	x	x	
Ciprofloxacin 500 mg po (or equivalent)			x				x	
Focused Physical Exam			x				x	

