4. METHODOLOGY

4.1 STUDY DESIGN

This is a single site, proof of concept feasibility study to describe the effect of GTx-024 3 mg in postmenopausal female subjects with SUI. Postmenopausal will be defined as clinically confirmed female subjects who have undergone the onset of spontaneous, medical or surgical menopause prior to the start of this study. Durability of treatment will also be explored by evaluating validated measures at 4 weeks after last dose. Up to 35 subjects will be enrolled in this study.

Institutional Review Board (IRB) approval from Beaumont's Human Investigations Committee will be obtained prior to beginning any study activity. Once IRB approval is obtained, potential participants will be identified from existing medical records, or physician or other referrals.

Potential subjects may be prescreened by telephone prior to the first in person study visit (initial screening visit). At the first in person study visit, subjects will be seen in the Urology Clinical Research space and informed consent will be obtained prior to any study activity. At Study Visit, 2, inclusion/exclusion criteria will be verified, study data will be collected, and consented participants may begin treatment.

Enrolled subjects will agree to maintain on a stable dose of any medication known to affect lower urinary tract function, including but not limited to anticholinergics, tricyclic antidepressants, or alpha-adrenergic blockers, throughout the treatment and follow-up period. Subjects enrolled in the study will agree to not start any new treatment (medication or otherwise) that is known to affect lower urinary tract function throughout the treatment and follow up periods. Subjects will also agree to refrain from performing any Kegal exercises and maintain current dietary habits throughout the treatment and follow up periods.

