7.2 EARLY TERMINATION

Subjects may withdraw from the study voluntarily. In addition, if the PI determines that continued participation might present a safety risk for the subject then the PI may withdraw the subject from the study. Those subjects who receive study drug will be followed for 28 days after stopping study participation. Every effort will be made to obtain all end of treatment measures as outlined in (Table 1.Visit 6) in the event that a subject withdraws, or is withdrawn, from the study before completing treatment.

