Repeated measures (mixed models) will be used to examine the change over time by incorporating all available assessment times to test for a significant non-zero slope over time and estimate that slope and its standard error.

Various imputation methods may be explored if any of the above analyses indicate promise for the compound in the treatment of SUI. These imputation methods may allow for better estimation of effect size and consequently sample size estimation in future trials.

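### Is a cap of 35 too small to give 30 completers under the plan's own 10-20% withdrawal range?

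*Combined protocol and SAP*

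**What the plan says.** Section 10 (Statistical Considerations) opens with the basis for the sample size: "Since this is a proof of concept feasibility study, no power calculation is needed". It then cites an earlier phase II trial of the drug for the expectation that "10-20% of patients may withdraw from the study before completing treatment", and the next sentence draws the enrolment rule from it: "we will recruit up to 35 patients meeting inclusion/exclusion criteria until 30 subjects have completed treatment".

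The Protocol Summary repeats the rule without a withdrawal rate: "up to 35 subjects meeting inclusion/exclusion criteria will be recruited until 30 subjects have completed treatment". Section 4.1 gives only the ceiling: "Up to 35 subjects will be enrolled in this study". No section names a single planning rate within 10-20%, and none says what follows if 35 are enrolled and fewer than 30 complete.

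**The concern.** Section 10 presents the withdrawal range as the reason for the cap, so a reader may take 35 as enough for 30 completers anywhere in that range. It is not. At 20% withdrawal, 30 expected completers would need 37.5 enrolled, and 35 gives 28.

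The number of completers matters to the primary analysis. Section 10.1 tests the change in stress leaks per day from Baseline to Week 12, and Section 10 rules out imputation. A subject without a Week 12 diary therefore drops out of that test. If the cap were a miscalculation, the trial could end smaller than its sponsor intended, and a final count of 28 or 29 might be read as a missed target.

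**Working it through.** **Inputs.** Withdrawal rate d = 10% to 20% (Section 10). Ceiling 35 and target 30 (Section 10 and Protocol Summary). Enrolment period 6 months and treatment 12 weeks (Protocol Summary). Assumption: withdrawals are independent with a common rate.

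**1. Reproducing the cap.** Enrolment for an expected 30 completers is 30/(1 - d).
- d = 10%: 30/0.90 = 33.3
- d = 15%: 30/0.85 = 35.3
- d = 20%: 30/0.80 = 37.5

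The rate at which 35 is exactly right is 1 - 30/35 = 14.3%. Simple inflation at the midpoint, 30 × 1.15 = 34.5, also rounds up to 35. The figure is therefore recovered near the middle of the stated range. It falls short only above 14.3%.

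**2. Expected completers if all 35 are enrolled.** 35 × (1 - d), with the chance of at least 30 from X ~ Binomial(35, 1 - d):

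| Withdrawal | Expected completers | P(X ≥ 30) |
|---|---|---|
| 10% | 31.5 | 87% |
| 14.3% | 30.0 | 62% |
| 15% | 29.75 | 57% |
| 20% | 28.0 | 27% |

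**3. Does the stop at 30 change this?** With even accrual over 6 months (about 26 weeks), the share enrolled at least 12 weeks before the last entry is (26 - 12)/26 = 54%, or 35 × 14/26 ≈ 19 subjects. At most about 19 could have completed when the 35th enters, so the stop would not act and step 2 applies. If accrual were slow enough for the stop to act at once, completers would be min(30, X), with expectation 29.8 at 10%, 29.0 at 15% and 27.8 at 20%. Both readings give about 28 at the upper end.

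**4. Cost in precision.** The standard error of a mean change scales as 1/√n. Relative to 30 completers:
- 15%: √(30/29.75) = 1.004
- 20%: √(30/28) = 1.035

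**5. What a larger cap would buy.** At 20% withdrawal, 38 enrolled gives 38 × 0.80 = 30.4 expected completers and a 66% chance of at least 30. A chance above 90% needs 42 enrolled (94%; 41 gives 89.8%). Covering the worst end of the range thus means up to seven more women on an investigational drug, to avoid a standard error about 3.5% wider.

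**The case for a change.** The best case for a change is that the plan itself ties the cap to the whole 10-20% range and then does not honour the upper part of it. Reaching 30 is not much better than even odds at the midpoint (57%) and is unlikely at 20% (27%), yet Section 10 does not say so. Two short sentences would remove the mismatch.

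The provisions that might soften the loss are also weaker than they look. Section 7.2 promises that "Every effort will be made to obtain all end of treatment measures" from subjects who leave early, but it points to Visit 6 of Table 1. That is a telephone and mail contact with no voiding diary; the end-of-treatment diary is at Visit 5. The mixed models "incorporating all available assessment times" are an exploratory analysis of slope, so they do not restore a missing Week 12 change to the primary signed-rank test.

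All of this is factually right. The arithmetic stands, and neither provision should be counted on to recover lost observations, so the 3.5% in the working takes no credit for them. What does not follow is that the plan needs changing. The withdrawal range is worded as a possibility, and planning near its middle is ordinary practice. The range and the cap sit in adjacent sentences, so a reader can see what 20% implies. A ceiling combined with a target already allows enrolment to end with the target unmet, and a note saying so would restate the rule.

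**Conclusion.** No change follows. The cap of 35 is a defensible figure: it matches 14.3% withdrawal, inside the stated range, and is within one patient of the need at 15%. At the 20% extreme the expected shortfall is two completers and the standard error is about 3.5% wider than with 30. In an open-label, single-arm feasibility study with no power statement, no success threshold and descriptive summaries supported by unadjusted tests, that difference would not alter any conclusion. Results from 28 or 29 completers would be as sound as results from 30, provided the report gives the number completing and the reasons for withdrawal. Section 5.4.1 already requires the reasons to be reported.

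This rests on the 10-20% range as the plan states it (the cited trial was not checked), on independent withdrawals at a common rate, and on completers having a usable Week 12 diary. A sponsor revising the document for other reasons could name a planning rate of about 14-15%, but the cap, stopping rule and analyses would stay as they are.

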1 PROTOCOL SUMMARY

Title:	GTx-024 as a Treatment for Stress Urinary Incontinence in Women: A Proof of Concept Study
Sponsor:	GTx, Inc.
Indication:	Stress Urinary Incontinence (SUI)
Study Design:	This is a single site, single-arm, open-label proof of concept feasibility study.
Objectives:	
Primary Objective Describe the effect of 12 weeks of treatment of GTx-024 on the number of stress incontinence episodes/day as assessed by the 3 day voiding diary.
 
Secondary Objectives Describe the effect of 12 weeks of treatment of GTx-024 on the number of voids/day as assessed by the 3 day voiding diary.
 
Describe the effect of 12 weeks of treatment of GTx-024 on urine volume per void as assessed by the 3 day voiding diary.
 
Describe the effect of 12 weeks of treatment of GTx-024 on SUI as assessed by 24 hour pad weight test.
 
Describe the effect of 12 weeks of treatment of GTx-024 on SUI as assessed by the Urethral Pressure Profile (UPP).
 
Describe the effect of 12 weeks of treatment of GTx-024 on SUI as assessed by the Bladder Stress Test.
 
Describe the effect of 12 weeks of treatment of GTx-024 on patient reported stress urinary incontinence symptoms as assessed by the MESA Urinary Questionnaire.
 
Describe the effect of 12 weeks of treatment of GTx-024 on patient reported impression of stress urinary incontinence severity as assessed by the Patient Global Impression of Severity Scale (PGI-S)
 
Describe the effect of 12 weeks of treatment of GTx-024 on patient reported impression of improvement as assessed by the Patient Global Impression of Improvement Scale (PGI-I).
 
Describe the effect of 12 weeks of treatment of GTx-024 on patient reported urogenital distress as assessed by the Urinary Distress Inventory Questionnaire (UDI-6).

	
Describe the effect of 12 weeks of treatment of GTx-024 on patient reported impact of urinary incontinence on daily life as assessed by the Incontinence Impact Questionnaire (IIQ-7).
 
Describe the effect of 12 weeks of treatment of GTx-024 on patient reported sexual function as indicated on the completion of the Female Sexual Function Index Questionnaire (FSFI).
 
Describe the effect of 12 weeks of treatment of GTx-024 on pelvic floor muscles as measured by MRI.
 
Safety objective: To describe the safety profile of GTx-024 3 mg PO daily in subjects with SUI.

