3. OBJECTIVES

3.1 PRIMARY OBJECTIVE

1. Describe the effect of 12 weeks of treatment of GTx-024 on the number of stress incontinence episodes/day as assessed by the 3 day voiding diary.

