concomitant meds and adverse events, including any vaginal bleeding, discharge, infections and/or spotting, will be assessed and recorded. Subjects will also be instructed to complete a 24 hour pad weight and 3 day voiding diary in the week preceding their next study visit. A 30 day supply of study drug will be dispensed with administration instructions.

Study Visit 4: Week 8, Clinic Visit

Approximately 8 weeks after beginning treatment, subjects will return to the clinical research office for an in person visit. An interview and vital signs will be conducted. Height and weight and PVR will be measured. Pad weights will be measured, and the 3 day voiding diary will be collected and reviewed. Blood will also be drawn to measure serum AST, ALT, and total bilirubin. Questionnaires will also be completed and concomitant meds and adverse events including any vaginal bleeding, discharge, infections and/or spotting, will be assessed and recorded. Subjects will also be instructed to complete a 24 hour pad weight and 3 day voiding diary in the week preceding their next study visit. A 30 day supply of study drug will be dispensed with administration instructions.

Study Visit 5: Week 12, Clinic Visit

Approximately 12 weeks after beginning treatment, subjects will return to the clinical research office for an in person visit. An interview with vital signs will be conducted. A focused physical exam will be done. Gynecological pelvic exam will only be done at this visit if clinically indicated. Urine dipstick will be done and PVR will be measured. Height and weight will be measured. 24 hour pad weights and 3 day voiding diaries will be collected/reviewed. Blood will also be drawn to measure laboratory values as outlined in Table 1. UPP, Bladder Stress Test, and MRI will be performed at end of treatment, questionnaires will be administered, and concomitant medications/adverse events will be assessed and recorded. All study medication will be collected and accounted for.

Study Visit 6: Week 16, Telephone/mailed questionnaire visit

Approximately 4 weeks after study drug treatment has ended, subjects will be contacted by phone to assess for concomitant meds and adverse events. Subjects will also be instructed to complete and return mailed questionnaires.

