Mammography is the process of using low-energy X-rays to examine the human breast, which is used as a diagnostic and screening tool. The goal of mammography is the early detection of breast cancer, typically through detection of characteristic masses and/or microcalcifications.

Magnetic Resonance Imaging(MRI)

MRI will be done at baseline and end of treatment to observe changes in pelvic floor muscles along with the thickness of the endometrium (mm). Quantitative assessments may include the area of the levator, the anteroposterior and transverse diameters, and/or other relevant parameters. Endometrial thickness can accurately be assessed by MRI (Stanislavsky, Weerakkody, et al., 2015; Nakamura et al., 2014); therefore, it is being used as a safety assessment in this study.

Medical, Epidemiological and Social Aspects of Aging (MESA) Questionnaire

The MESA questionnaire measures severity of specific types (stress, urgency, mixed) of urinary incontinence (UI). Two subscales, the urgency UI (6 items) and the stress UI (9 items). Test-retest reliability on “any incontinence” is high (agreement coefficient = .89). Validity (agreement between self-report on the MESA and clinician’s assessment) = 87% in women. The MESA questionnaire has demonstrated agreement on incontinence = 79% and 69% and 72% accuracy in predicting urodynamic diagnosis of stress UI and uninhibited detrusor contraction (Herzog, 1990a; Herzog, 1990b).

3 Day Voiding Diary

Subjects will record each episode of urinary leakage and record its severity. Subjects will also be asked to record urinary frequency, and urgency. Urine volume will also be recorded. 3 day bladder diaries are reliable measures of mean number of UI episodes/day, UI type, mean voids/24 hours, and mean voids during sleeping hours. 2-week test-retest results correlate with diurnal micturition ($r=.89$, $p<0.001$) and UI episodes ($r=.91$, $p<0.001$). Compared to participant recall of the previous week, Spearman rank correlation = .57 for voiding frequency and .70 for UI episodes (Brown, 2003; Locher, 2001; Wyman, 1988). For this study, any episode of vaginal discharge or spotting will also be recorded on the diary.

Patient Global Impression of Improvement (PGI-I)

PGI-I is a global rating of improvement using 7-point scale. Construct validity was established in two randomized controlled studies ($n=1,133$ subjects) of drug treatment for predominant stress incontinence (Wagner, 1996; Yalcin, 2003).

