9. ASSESSMENT OF SAFETY

9.1 METHODS AND TIMING FOR ASSESSING, RECORDING, AND ANALYZING SAFETY PARAMETERS

9.1.1 ADVERSE EVENTS

ICH E6 defines an AE as any untoward medical occurrence in a subject or clinical investigation subject administered a pharmaceutical product regardless of its causal relationship to the study treatment. An AE can therefore be any unfavorable and unintended sign (including an abnormal laboratory finding), symptom, or disease temporally associated with the use of a medicinal (investigational) product, whether or not considered related to the medicinal (investigational) product.

The occurrence of an AE may come to the attention of study personnel during study visits and interviews of a study subject presenting for medical care, or upon review by a study monitor.

The period of observation for which AEs are to be collected begins after the subject has signed the ICF, throughout the study intervention period, and for 28 days post treatment.

All AEs, whether reported by the subject or noted by study personnel, will be recorded in the subject's medical record and captured on the appropriate CRF.

Information to be collected includes event description, time of onset, Investigator's assessment of severity, Investigator's assessment of relationship to study drug, and time of resolution/stabilization of the event. All AEs occurring while on study must be documented appropriately regardless of relationship to study drug. All AEs will be followed to adequate resolution as per [Section 9.3 TYPE AND DURATION OF FOLLOW-UP OF SUBJECTS AFTER ADVERSE EVENTS](#).

Any medical condition that is present at the time that the subject is screened will be considered as baseline and not reported as an AE. However, if the condition deteriorates at any time during the study, it will be recorded as an AE. All AEs must be graded for intensity and relationship to study drug.

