9.3 TYPE AND DURATION OF FOLLOW-UP OF SUBJECTS AFTER ADVERSE EVENTS

AEs will be collected up until 28 days after the last dose of study treatment, and will continue to be followed up until one of the following occurs:

Resolved or improved to baseline

Death

Investigator confirms that no further improvement can be expected

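### The stated safety report covers only adverse events during treatment: it leaves out the 28-day follow-up events and gives no summary of measured liver tests, lipids or endometrial thickness

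*Combined protocol and SAP*

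**What the plan says.** The safety objective in the Protocol Summary is broad: "To describe the safety profile of GTx-024 3 mg PO daily in subjects with SUI".

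The planned report is narrower. Section 10 states: "Safety will be reported by the number and type of adverse events reported during treatment". The Statistical Considerations row of the Protocol Summary has almost the same sentence: "Safety will be determined by the number and type of adverse events reported during treatment". Nothing else in Sections 10 or 10.1 describes a safety analysis.

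Collection runs longer than the report. Section 9.1.1 starts AE collection at consent and continues it "throughout the study intervention period, and for 28 days post treatment". Section 9.3 agrees: "AEs will be collected up until 28 days after the last dose of study treatment". Section 9.2.1 applies the same 28 days to SAEs. The Week 16 visit in Section 7.1 is partly a safety contact: "Approximately 4 weeks after study drug treatment has ended, subjects will be contacted by phone to assess for concomitant meds and adverse events".

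Safety measurements other than AEs are also scheduled. Section 2.2.1 attributes a dose-dependent ALT rise and a dose-dependent fall in HDL to the drug, and Section 2.2.3 gives possible ALT elevation as the reason for liver monitoring. Section 8 says of endometrial thickness on MRI: "therefore, it is being used as a safety assessment in this study".

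**The concern.** The protocol collects safety information over one period and in several forms, then states a report that covers a shorter period and only one form. This is an express rule given twice, so it is more than missing detail.

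Two things are at stake. First, an event that begins after the last dose has no place in the stated result. On a literal reading, neither does one that begins in the last days of treatment and is first reported at the Week 16 call. Second, a shift in ALT or HDL, or a change in endometrial thickness, would be seen only through individual values recorded as AEs. A general fall in HDL across the group, with no single value recorded as an AE, would not appear at all. Either gap leaves the safety objective only partly answered.

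**Working it through.** The plan gives no figure to reproduce here. The check is a comparison of texts, with one piece of arithmetic.

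**Step 1: the AE window.**
- Collected: from consent, through treatment, to 28 days after the last dose (Sections 9.1.1 and 9.3; Section 9.2.1 for SAEs).
- Reported: during treatment (Section 10 and Protocol Summary).
- Difference: AEs between consent and first dose, and AEs in the 28 days after the last dose.

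**Step 2: size of the follow-up part.** Treatment lasts 12 weeks (Section 3.1), and follow-up lasts 28 days.
- Treatment days: 12 × 7 = 84
- Planned days from first dose: 84 + 28 = 112
- Share outside treatment: 28 / 112 = 25%

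This is a share of planned days for a subject who completes treatment. The documents give no post-treatment event rate, so it cannot be turned into a number of events or subjects.

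**Step 3: measured data against the analysis text.**

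| Measure | When collected (Table 1) | Why it bears on safety | Analysis in Sections 10 and 10.1 |
|---|---|---|---|
| ALT, with AST and total bilirubin | Screening, Weeks 4, 8, 12 | ALT rise named as a drug effect (2.2.1); monitored for that reason (2.2.3) | None |
| Lipid panel | Baseline, Week 12 | HDL fall named as a drug effect (2.2.1) | None |
| Endometrial thickness by MRI | Before first dose, Week 12 | Designated a safety assessment (Section 8) | None; the MRI analyses cover pelvic floor muscles only |

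Table 1 has no liver draw at Week 0, so the screening value is the only pre-treatment one.

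**Step 4: other text that might fill the gap.**
- The Week 12 to 16 comparison in Section 10.1 concerns durability of treatment and names no safety analysis.
- The liver thresholds in Section 9.4 guide decisions about individual subjects. They do not define a summary.
- Section 9.1.1 lets an abnormal laboratory finding count as an AE. That brings in some values, but not the distribution of values or the change from baseline.

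**The case against.** The best reply is that little is really lost. Follow-up AEs go on the case report form and are followed up under Section 9.3. SAEs to 28 days are reported within 24 hours and appear in expedited or annual reporting under Section 9.2. Neither safety sentence says that nothing else will be reported, and the heading of Section 9.1 speaks of analysing safety parameters, so the reference to treatment may be loose shorthand. Section 2.2.1 also suggests that drug-related effects resolve on stopping, so follow-up events may be few.

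On laboratory values, Section 9.1.1 includes abnormal findings in the AE definition and requires every AE to be recorded. Section 9.1.2 has a mild grade that covers asymptomatic observations. Recording is therefore not at the investigator's whim. Finally, this is an uncontrolled proof-of-concept study of up to 35 subjects, and which laboratory tables to specify is partly a matter of taste.

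Much of this stands. The issue is what the safety result will contain. Oversight of subjects is not in doubt. But expedited and annual reporting are not the study's safety analysis, and the two sentences are the only statement of what that analysis is. If they are shorthand, they should be corrected. The AE route still depends on a judgement that a given value is an AE, and it cannot show a shift in the group. Small size argues for simple descriptive tables, which is all that is proposed here.

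**Conclusion.** The point holds. The stated safety report leaves out AEs and SAEs from the 28-day follow-up. It also gives no summary of measured ALT, AST and bilirubin, of lipids including HDL, or of endometrial thickness, except where a value is recorded as an AE during treatment. The follow-up gap is 28 of 112 planned days (25%) from first dose. This rests on reading both sentences as written, on full 12-week treatment, and on the lipid panel including HDL.

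Four stronger readings are tempting, and the documents do not support them:

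- That a quarter of events would be missed. The 25% counts days, and no post-treatment event rate is given.
- That the 20.8% ALT rate in Section 2.2.1 shows how many cases would be missed. That figure comes from a table of reported AEs, so such cases arising during treatment would be counted under the stated rule. The rate of ALT rises not recorded as AEs is not given.
- That endometrial thickening is a known drug risk. The protocol designates thickness a safety assessment and uses it for eligibility, but nowhere names thickening as an effect of the drug.
- That safety data would go uncollected or unseen. They are collected and followed; what is missing is their place in the analysis.

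**What to change.** Change the safety sentence in Section 10 and its twin in the Protocol Summary so that AEs and SAEs are reported from first dose to 28 days after the last dose. Show on-treatment and follow-up events separately, and list events between consent and first dose.

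Add to Section 10.1 descriptive summaries from data already scheduled:

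- ALT, AST and total bilirubin at screening (named as baseline) and at Weeks 4, 8 and 12, with counts above the multiples of the upper limit of normal that Section 9.4 already uses: 3, 5 and 8 for ALT or AST, and 2 for bilirubin. They serve here only as reporting cut-points.
- Lipids, including HDL, as change from Baseline to Week 12.
- Endometrial thickness, as change from the pre-treatment MRI to Week 12.

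The cost is two amended sentences and a few extra descriptive tables. No new visit, sample, test or clinical rule is needed.
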